### Key Secondary Hypothesis

Hypothesis: Treatment with LEV improves the rate of seizure cessation at 48 hours in neonates compared with standard PB treatment.

Analysis Plan: A similar approach as used for the primary outcome will be utilized to analyze the 48 hours seizure cessation rates.

## 7.4 Analysis of Remaining Secondary Outcomes

- Hypothesis 1: Treatment with LEV improves the rate of seizure cessation at 1 hour in neonates compared with standard PB treatment.

Analysis Plan: A similar approach as used for the primary outcome will be utilized to analyze the 1-hour seizure cessation rates.

- Hypothesis 2: Length of seizure freedom will be longer in the LEV group than in the PB group.

Analysis Plan: Actual length of seizure freedom will be summarized by mean and standard deviation as well as quartiles. Comparison between randomization groups will be performed using Wilcoxon-rank sum test.

- Hypothesis 3: Additional LEV treatment in neonates who didn't respond to 40mg/kg LEV will be effective (additional seizure terminations).

Analysis Plan: The percentage of neonates whose seizures stop following 60mg/kg LEV, having not responded to 40mg/kg LEV will be calculated with the corresponding 95% confidence interval.

- Hypothesis 4: LEV treatment will result in a lower dose of phenobarbital being needed as compared to the PB treatment alone.

Analysis Plan: Phenobarbital dose will be summarized by mean and standard deviation as well as quartiles. Comparison between randomization groups will be performed using Wilcoxon-rank sum test.

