Because neonatal seizures are very frequently entirely subclinical it is accepted that continuous EEG monitoring is the only way to adequately detect neonatal seizures and the only objective means to judge the

response to AED treatment^{5, 24, 25} Murray et al. reported in a video EEG study that only 34% of electrographic seizure events in encephalopathic newborns are clinically identified and only 9% were recognized by nurses at the bedside²⁶. Lawrence et al. noted that more than 90% of EEG seizures had no clinical correlate²⁷. Despite this, continuous EEG monitoring is not standard of care for neonates at risk of seizures in the majority of NICUs in the United States and internationally. This is due largely to the lack of available resources to conduct and review continuous EEG monitoring. Conventional full neonatal montage EEG requires specialist review. In each hospital center there are insufficient neurologists to provide a service of real time review of the data 24 hours a day.

Recent EEG data software developments now allow for remote review of full montage continuous EEG data securely via the internet. This opens the door to the development of a centralized system for review of continuous neonatal EEG data by neurologists.

There would be great value in a reliable automated seizure detection method but such algorithms are not in widespread use for real time neonatal seizure detection. Automated detection of electrographic seizures in the newborn requires different techniques from those employed in adults and must be developed and tested specifically in neonates. Existing algorithms have been shown to have sensitivities of between 43 % to 63% and specificities between 56% to 90%, not high enough for use in a clinical environment^{27, 28}.

7. PROGRESS REPORT/PRELIMINARY STUDIES:

Preliminary Validation data for Automated seizure detection algorithm

In testing against a large dataset of 114 hours of EEG from 87 neonates, including 389 seizures from 55 seizure-affected neonates, the August 2010 alpha version of Persyst's neonatal seizure detector demonstrated an overall seizure detection sensitivity of 79%, a seizure-affected patient detection rate of 98% (i.e., at least one seizure correctly detected in an infant who is experiencing seizures), and a false positive rate of approximately 1 detection per 11 hours monitoring.

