Patient baseline characteristics: Eighteen patients received treatment with intravenous LEV, 6 at the first dosing level and 12 at the higher dose. There were 9 male and 9 female patients. The weight of subjects ranged between 2.5 and 4.7 kg. All subjects had a gestational age between 37 and 41 weeks. In 8 subjects the underlying etiology of seizures was hypoxic ischemic encephalopathy. 5 of these subjects received hypothermia treatment during the study period. 2 subjects were found to have ischemic stroke, 2 subjects had intraventricular hemorrhage. 1 subject had a complex brain malformation with polymicrogyria, hypoplastic brainstem and cerebellar vermis with a Dandy Walker malformation. In 4 subjects the etiology of seizures was unknown despite investigation with brain MRI, sepsis screen, lumbar puncture and extensive metabolic investigations.

[figure not shown]
Table 1

	Mean	SD	Median	Min	Max
Vd (L/kg)	1.01	0.13	0.98	0.81	1.24
CL Day 1 (L/h/kg)	0.042	0.016	0.039	0.023	0.085
CL Last Day (L/h/kg)	0.080	0.021	0.080	0.053	0.142
T1/2 Day 1 (h)	18.5	7.1	15.6	8.8	32.7
T1/2 Last Day (h)	9.1	2.0	9.0	5.3	12.7

Pharmacokinetic results:

The final PK data set contained 149 observations from the 18 subjects. Urine collections were completed in 18 subjects. Table 1 summarizes the PK parameters calculated and Figure 1 shows the raw pharmacokinetic data.

Figure 1.

Adverse events and safety monitoring: Patients were reviewed daily to evaluate for possible adverse clinical events related to LEV treatment. LEV was well tolerated. Only one serious adverse event occurred in this study. One subject with a brain malformation and a high Phenobarbital level required intubation while on treatment with LEV. LEV was not thought to be causal of this event.

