EEG data monitoring and automated seizure detection: Gold standard 9 channel neonatal montage continuous video-EEG data will be collected for 24 to 48 hours after study drug administration with the length of monitoring time determined by the Principal Investigator for each site. There may be infants who, after 24 hours of remaining seizure-free, are appropriate for discontinuation of monitoring which also may enable them to be safely discharged home. Babies undergoing hypothermia for hypoxic ischemic encephalopathy will have EEG monitoring data captured for 24 hours post start of rewarming as this is a high risk time for seizures. Each site will use available video EEG equipment with Persyst software installed. A research dedicated Cadwell video EEG system is requested under this grant for each site. Following recruitment to monitoring, each site will have their study investigator monitoring the EEG in real time, per the study algorithm. Corticare technicians will provide continuous EEG monitoring by remote access to the acquisition station. If Corticare or the real time onsite observer detects seizure activity the site investigator or local encephalographer will immediately be contacted to review the tracing. Neonatal EEG data obtained from conventional digital EEG machines based at the study sites will be monitored in near- real time using Persyst Insight software running

on the acquisition stations via the site's local area network or remotely via secure Internet access utilizing Citrix server, Microsoft Remote Desktop, or similar institutional remote access capabilities. The EEG data will be continuously analyzed in near- real time using Persyst MagicMarker in order to produce and display EEG data trend graphs. The graphical EEG trends will include Rhythmic Run Detection and Display, amplitude integrated EEG, FFT spectrograms, asymmetry spectrograms, and other trends useful in the rapid recognition of seizures. Following completion of the local study on each subject the full video EEG (totalling 5 Gigabytes of data/ 24 hours) will be archived on the UCSD server for analysis by the encephalographers. Data transfer will be achieved where possible by encrypted internet connections. Alternatively the studies will be mailed on memory sticks or DVDs. Archived video continuous EEG data will be available for trend analysis and seizure detection comparison with the duplicate formal encephalographers reading of the 48 hours of tracing.

Add on Study:

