### 3.4 Power and Sample Size Determination

Power calculations were based on a 2-sided chi-square test for detecting a difference between two proportions, assuming a Type 1 error of 0.05. With a sample size of 60 LEV subjects and 40 PB subject and assuming a seizure cessation rate of 50% in the control arm, we have 80% power to detect a seizure cessation rate as low as 22% (an absolute difference in seizure outcome rates of 28% or greater) in the LEV group.

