### 4.3 Other Secondary Outcomes

- Seizure termination at 1 hour after treatment.
- Dose escalation - Seizure termination at 24 hours following 60mg/kg LEV, having not responded to 40mg/kg.
- Length of seizure freedom.
- Phenobarbital dose

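### Length of seizure freedom has no event definition or censoring rule although EEG may stop from 24 hours; if times run to the end of EEG, the planned mean and Wilcoxon test understate it and can lose power

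*SAP*

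**What the plan says.** **Follow-up.** Protocol section 8 (EEG data monitoring and automated seizure detection) says that EEG "will be collected for 24 to 48 hours after study drug administration with the length of monitoring time determined by the Principal Investigator" at each site. It expects some "infants who, after 24 hours of remaining seizure-free, are appropriate for discontinuation of monitoring which also may enable them to be safely discharged home". Cooled infants follow a different clock, with "EEG monitoring data captured for 24 hours post start of rewarming". Protocol section 6 (Barriers to Detection of Neonatal Seizures) holds that "continuous EEG monitoring is the only way to adequately detect neonatal seizures".

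**Outcome.** SAP 4.3 gives only a name, "Length of seizure freedom". It states no time zero, event, horizon or censoring rule.

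**Analysis.** SAP 7.4, Hypothesis 2, predicts longer seizure freedom on LEV. Its plan reads "Actual length of seizure freedom will be summarized by mean and standard deviation as well as quartiles", followed by a Wilcoxon rank-sum test. The SAP contains no event indicator, Kaplan-Meier curve or log-rank test. SAP 6.2 tests secondary outcomes at two-sided 0.05 without adjustment.

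**Related outcome.** The 48-hour key secondary (SAP 7.3) is analysed like the primary. SAP 6.1 defines ITT as everyone randomized. Neither document says how an infant without 48-hour EEG is scored.

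**The concern.** Length of seizure freedom is a time-to-event outcome, but the SAP treats it as fully observed. By the protocol's own account, seizure freedom cannot be reliably established once EEG ends. For an infant with no recurrence, the time to the end of EEG is therefore only a lower bound on the true time.

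If that lower bound is entered as the length, two things follow:

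- Means and quartiles understate seizure freedom. The arm with more responders loses more, so the arm difference shrinks.
- The Wilcoxon test ranks equally event-free infants by how long a site kept EEG running, which is noise. It also places an infant taken off EEG seizure-free at 24 hours below one who seized at hour 30.

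At stake is one of four outcomes listed in SAP 4.3. The scoring of the 48-hour key secondary shares the same gap.

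**Working it through.** **1. The plan's own figure.** SAP 3.4 gives 80% power for 60 LEV v 40 PB infants, "assuming a seizure cessation rate of 50% in the control arm" and 22% on LEV. It applies to the binary cessation endpoint; no power is stated for length of seizure freedom.

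- Pooled rate = (40 x 0.50 + 60 x 0.22)/100 = 0.332.
- Null SE = sqrt(0.332 x 0.668 x (1/40 + 1/60)) = 0.0961.
- Alternative SE = sqrt(0.25/40 + 0.1716/60) = 0.0954.
- Power = Phi((0.28 - 1.96 x 0.0961)/0.0954) = Phi(0.96) = 83%. Fisher's exact test by enumeration gives 79.6%.

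The stated 80% is sound for that endpoint.

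**2. Inputs for this outcome.** From the documents: 60 v 40, two-sided 0.05, 22% v 50%, EEG end at 24 to 48 h. Assumed, because the documents give no values:

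- the share of infants stopped early, equal in both arms unless stated;
- 22% v 50% read as 24-hour rates, with 18% v 42% at 48 h;
- a benefit case of 78% v 50% at 24 h and 75% v 45% at 48 h;
- recurrences before 24 h exponential (6 h scale) truncated at 24 h, later ones uniform over 24-48 h.

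**3. Mean difference.** The mean early recurrence time is 6 - 24e^-4/(1 - e^-4) = 5.55 h, and the mean late time is 36 h.

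*SAP 3.4 rates, everyone on EEG to 48 h*
- PB: 0.50 x 5.55 + 0.08 x 36 + 0.42 x 48 = 25.8 h.
- LEV: 0.78 x 5.55 + 0.04 x 36 + 0.18 x 48 = 14.4 h.
- Difference 11.4 h (11.3 h in simulation).

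*SAP 3.4 rates, half stopped at 24 h*
- PB: 2.78 + 0.25 x 24 + 0.5 x (2.88 + 20.16) = 20.3 h.
- LEV: 4.33 + 0.11 x 24 + 0.5 x (1.44 + 8.64) = 12.0 h.
- Difference 8.3 h.

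The same steps in the benefit case take the difference from 12.1 h (38.3 v 26.2) to 8.6 h (29.1 v 20.5).

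**4. Power.** 10,000 simulated trials per scenario. Wilcoxon uses the earlier of recurrence and EEG end, log-rank is censored at EEG end, and the capped Wilcoxon uses the earlier of recurrence and 24 h.

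| Scenario | Planned Wilcoxon | Log-rank | Wilcoxon capped at 24 h |
|---|---|---|---|
| Benefit, all to 48 h | 85% | 87% | 81% |
| Benefit, 25% stopped at 24 h | 76% | 86% | 81% |
| Benefit, half stopped at 24 h | 72% | 84% | 80% |
| Benefit, EEG end spread evenly over 24-48 h | 68% | 85% | 81% |
| Benefit, 28% cooled (EEG end 48-96 h), half of the rest stopped | 71% | 86% | 81% |
| Benefit, only non-recurrers stopped | 74% | 87% | 82% |
| Benefit, all stopped at 24 h | 82% | 84% | 82% |
| SAP 3.4 rates, all to 48 h | 67% | 76% | 67% |
| SAP 3.4 rates, half stopped | 67% | 78% | 68% |

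The 28% is 5/18: in the pilot (Protocol section 7), "5 of these subjects received hypothermia treatment during the study period". Those infants were phenobarbital-refractory, so the share is only illustrative.

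Repeat simulations agree within about 2 points: 85-87% with full EEG, 71-73% with half stopped, and 84-85% for log-rank with half stopped. Stopping only 5-10% costs about 2 to 6 points. A different recurrence model (78% v 50% at 24 h, 70% v 40% at 48 h) gives 88% with full EEG, 76% with half stopped and 87% for log-rank. Under no treatment effect with equal stopping, the Wilcoxon test rejects in 4.7-5.1% of trials.

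**5. Source of the loss.** In the benefit case with half stopped, correcting only the inversions against 24-48 h recurrences lifts Wilcoxon power from 72% to about 76%. With no recurrences after 24 h at all, power still falls from about 81% to 68-70%. Most of the loss therefore comes from ranking event-free infants by EEG length.

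**6. The 48-hour rate.** Assume 50% free at 24 h, 45% at 48 h, and half of the responders off EEG at 24 h.

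- Random stopping: unseen infants all failures, 0.225; all successes, 0.225 + 0.25 = 0.475; Kaplan-Meier, 0.5 x 0.225/0.25 = 0.45.
- Only non-recurrers stopped: 0.20, 0.45 and 0.5 x 0.20/0.25 = 0.40.

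The scoring rule alone spans 25 points.

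**The case against.** **The recording rule is inferred.** SAP 7.4 speaks of actual length without saying when it ends. Recurrence during the 5 protocol days counts as failure of the regime, and daily in-house examinations continue, so some information accrues after EEG. This stands as a reason to make the point conditional. It does not close the gap, since the protocol says that only continuous EEG detects these seizures adequately.

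**Early stopping may be rare.** The protocol says only that such infants may exist, and elsewhere refers to a formal reading of 48 hours of tracing. If few infants stop early, the loss is a few points. This stands.

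**No power is lost at the documents' own rates.** Correct. A reader might infer from the 67% v 76-78% at those rates that censoring is costly there. It is not: the gap is present with full EEG and reflects how the two tests weight the data. The material loss needs a LEV benefit, which is the direction of Hypothesis 2 but at assumed rates. The shrunken mean difference appears in both directions.

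**Inverted ranks are the whole problem.** A reader might infer this from the hour-24 v hour-30 example. Step 5 shows that they are the smaller part.

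**False positives.** A reader might infer an inflated type I error. In a hypothetical 30%/70% split of early stopping by arm, Wilcoxon error reaches 13-15% at a 50% response rate. The documents show no such imbalance, and blinding and randomization stratified by site make a large one less likely.

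**It is secondary.** True, and this limits the weight of the point.

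**Conclusion.** The gap is real and should be fixed. The outcome is undefined, follow-up varies at the site investigator's choice, and the named methods take no account of either.

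The size is conditional on times running to the end of EEG and on assumed stopping shares:

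- With half stopped at 24 hours, the mean difference shrinks by roughly a quarter to 30% (11.4 to 8.3 h at the SAP 3.4 rates; 12.1 to 8.6 h in the benefit case).
- If LEV is better at the assumed rates, Wilcoxon power falls from about 86% to 72%, while log-rank keeps about 85%. With 5-10% stopped the loss is a few points, and uniform stopping at 24 hours also costs little.
- At 22% v 50%, censoring costs almost no power.
- With equal stopping, type I error stays near 5%.

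A reader might infer that the trial's main result is at risk. The documents do not support that: EEG runs for at least 24 hours after study drug, so the 24-hour primary is largely unaffected. The 48-hour key secondary is exposed to the scoring rule, by an amount that depends on how many infants lack 48-hour EEG.

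**What to change.** **Length of seizure freedom (SAP 4.3 and 7.4)**
- Define it among treated infants, from a stated time zero to the first electrographic seizure or second anticonvulsant, censored at the end of EEG.
- Replace the mean and Wilcoxon test with Kaplan-Meier curves and a log-rank test, and report EEG duration by arm.
- State how death is handled, for example as a competing event or as failure. Ordinary censoring would be wrong in a population where the protocol expects substantial mortality and withdrawal of life support.
- Add a sensitivity analysis with all times capped at a common 24 hours, because stopping may be related to prognosis.

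**48-hour key secondary (SAP 7.3)**
- Count a second anticonvulsant by 48 hours as failure.
- State how infants without 48-hour EEG are scored.
- State how infants randomized but never treated are scored. Randomization can precede confirmed seizures, and Protocol section 10 reports about three monitored infants per treated one, so this group could be large under the ITT definition.
- Show best-case and worst-case bounds beside any Kaplan-Meier estimate.

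**Cost.** SAP wording, a standard survival analysis and the EEG stop time for each infant; no change to care. Kaplan-Meier assumes that stopping is unrelated to later recurrence. If only infants who would not recur are stopped, it gives 40% against a true 45% in the example. The 24-hour cap avoids that assumption but ignores later recurrences (81% power against 87% for log-rank with full EEG in the benefit case) and needs the 24-hour EEG minimum for every infant. The bounds may be wide.

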## 7.5 Analysis of Safety Outcomes

Adverse Event and Serious Adverse Events will be tabulated by randomization group and by drugs received, respectively. Details including seriousness, intensity, causality, withdrawal due to event and outcome will be summarized by frequencies and percentages by randomization group and by drugs received. Fisher's exact tests will be used to compare rates of adverse events, serious adverse events, study discontinuation and deaths between randomization group and by drugs received, respectively.

Findings will be tabulated by randomization group overall and for findings marked as AE and SAE, respectively.

Safety Labs (using DAIDS guidelines) will be presented with shift tables (hour 48 vs baseline) by randomization group and by drugs received, respectively.

